9.8.8 Data management

A NONMEM data set will be created from source data files provided by PRA for study MIT-Es0001-C302 and by Estetra for Es0001-C101 and (if used) MIT-Es0001-C103 and will undergo quality control (QC) review according to SOPs at the time of the finalization of the analysis plan.

The data manager will create one or more code files to automate the process of formatting the source dataset into the popPK dataset. No manual editing of the data will be done. The code file for the creation of the popPK datasets will be in R version 3.3.1 or later (R Foundation for Statistical Computing, Vienna, Austria).

A popPK data set can be very large. QC of the final NONMEM dataset will include manual comparison of a subset of the records to the source data (Sponsor or PRA provided datasets) as well as diagnostics on the entire dataset to identify errors. Diagnostics will also be performed to ensure that the dataset complies with the formatting standards for NONMEM. The QC may include review of the code used to generate the dataset, as appropriate. This QC will be done by personnel other than the data manager. Any discrepancies will be addressed. Revised datasets will undergo quality control to confirm that the expected changes (e.g., deleted data records) are correct. The scope of the QC will be dependent on the nature and complexity of the study, as well as the source data. Any unique or complicated formatting issues associated with the dataset will be flagged by the data manager for specific QC review.

9.8.9 Data Deletion

9.8.9.1 Missing Data

Incomplete data (e.g., missing dosing times) is a frequent occurrence in population analysis data sets. Typically, data with a missing or clearly erroneous dose time will be imputed per protocol or deleted as appropriate.

9.8.9.2 Erroneous Data

Data in the Sponsor data set will occasionally be found to be inconsistent with the known pharmacokinetics of the drug or study procedures. These may be a result of recording errors in the database (e.g., dose administered prior to study start or after study completion) or unrealistic pharmacokinetic considerations. These data may be deleted if they cannot be corrected based on data review and site queries.

9.8.9.3 Outliers

Outliers will be distinguished from erroneous data as being unusual but not inconsistent with the known pharmacokinetics of the drug. Outlier data may include entire subjects, entire subject visits, or individual observations. Outliers will be deleted only after careful examination of possible causes.

9.8.10 PopPK Model Development

Population pharmacokinetic model development will be performed in compliance with SOPs at the time of the finalization of the analysis plan.

9.8.10.1 Data Set Creation

Prior to initiation of analysis, NONMEM and other population PK software require specifically formatted data sets. Creation of these data sets is addressed Section 9.8.6.

9.8.10.2 Handling Data below the Limit of Quantification (BLQ)

BLQ data will be handled according to the "M3" methodology (Beal, 2001).

9.8.10.3 Model Development Procedures

A Bayesian analysis will be used to fit concentration-time data. Model features (number of compartments, lag times, covariate effects) will be included based on goodness of fit statistics (e.g., log-likelihood) and diagnostic plots. These pharmacokinetic models will be evaluated and used to derive individual post hoc pharmacokinetic parameters for E4 and DRSP described in Objectives (9.8.2).

Initial estimates of PK parameters (e.g., CL/F, V/F, Tlag) will be determined using exploratory compartmental analyses or previous PK analysis. These estimates will be employed to build an appropriate population PK model. The impact of individual characteristics on the PK parameters will be explored and included in the population model if significant.

9.8.11 PopPK Model Evaluation

A traditional approach to model selection will be used. In this approach, an initial simple model is run. Additional features are sequentially added to this model (e.g., compartments, lag times, variance terms, covariates), testing each addition for statistical significance, improvement of diagnostic graphics and/or biological plausibility. Model features (e.g., lag times, compartments) will be added or removed based on evaluation of diagnostic plots, consideration of biological plausibility, and statistical tests. The goodness-of-fit between hierarchical models is measured by the difference in the objective function value (OFV) produced by NONMEM. The difference in OFV between two hierarchical or nested models is approximately χ^2 distributed, with n degrees of freedom. As such, the OFV is used to obtain the significance level for the difference between two nested models. The criteria for forward addition will be p<0.05 and the criteria for backward elimination will be p<0.001. Covariate analyses will be performed separately for the PK of E4 and DRSP.

Assessment of model adequacy and decisions about increasing model complexity will be driven by the data and guided by goodness-of-fit criteria, including:

1. Visual inspection of diagnostic plots (e.g.,observed vs. predicted concentration, residual/weighted residual versus predicted concentration or time, and histograms of individual random effects).

2. Successful convergence of the minimization routine with at least 2 significant digits in parameter estimates. Successful minimization and covariance steps will be desired, but not required.

- 3. Plausibility of parameter estimates.
- 4. Precision of parameter estimates, if available.
- 5. Correlation between model parameter estimation errors < 0.95.
- 6. Likelihood ratio test.
- 7. Asymptotic and or Bootstrap estimate of confidence interval for parameter estimates.

Covariates to be considered during population pharmacokinetic model building include, but are not limited to, variables such as body weight, race, smoking, and fed vs fasted status. Pre-specified hypotheses will be examined first, followed by hypotheses generated from diagnostic plots. If applicable, this will be followed by an automated covariate search (SCM user guide).

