9.8.2 Objectives

The objectives are to assess the effect of various individual characteristics/covariates (e.g., body weight, race, smoking, and fed vs fasted status) on the pharmacokinetics (PK) of 15 mg Estetrol (E4)/3 mg Drospirenone (DRSP). As data permit, PK parameters will include, but are not limited to:

- Primary parameters (i.e. model parameters):
 - Apparent clearance (CL/F).
 - Central volume of distribution (V/F).
 - Lag time of Absorption (Tlag), if necessary.
 - Relative bioavailability for fed vs fasted state.
- Secondary parameters (i.e. derived parameters):
 - Maximum concentration (Cmax).
 - Time to Cmax (Tmax).
 - Extent of exposure for the dosing interval (AUCtau) at steady state.
 - Terminal half-life ($t^{1/2}$).
 - Predicted trough drug concentration (Ctrough) at steady state.
 - Distribution half-life $(t\frac{1}{2})$ (if applicable).

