9.8.4 Prespecified Hypotheses

Pre-specified hypotheses will be tested before any hypotheses that are based on diagnostic plots. Formal conclusions will be drawn only from these prespecified hypotheses. Results of other hypotheses (e.g., those based on diagnostic plots) will be considered exploratory and will not lead to conclusions.

- 1. Effect of body weight on volume of distribution of E4.
- 2. Effect of body weight on clearance of E4
- 3. Effect of race on clearance for E4.
- 4. Effect of smoking status on clearance for E4.

Protocol no: MIT-Es0001-C302

- 5. Effect of fed vs fasted state on rate (e.g. Ka) or extent (e.g., F) of absorption for E4.
- 6. Effect of body weight on volume of distribution of DRSP.
- 7. Effect of body weight on clearance of DRSP
- 8. Effect of race on clearance of DRSP.
- 9. Effect of smoking status on clearance of DRSP.
- 10. Effect of fed vs fasted state on rate (e.g. Ka) or extent (e.g., F) of absorption for DRSP.

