9.8.12.1 Report Structure

The popPK report will comprise the following sections:

1. Summary

- 2. Objectives and Hypotheses
 - a. Statement of the objectives of the analysis and formal statement of any hypotheses to be tested.
- 3. Assumptions
 - a. List of assumptions, with supporting data, as applicable. Assumptions will not be formally tested.
- 4. Materials and Methods
 - a. Data: description of data, to include (as applicable and appropriate) the number of individuals, number of observations, and range of sample collection times.
 - b. Data analysis methods:
 - i. The methods (e.g., forward addition/backward elimination) and criteria for model selection (likelihood ratio test, diagnostic plots).
- 5. Results
 - a. PopPK results
 - i. Data description: summary statistics including mean, median, and SD of continuous covariates, and distributions of discrete covariates.
 - ii. Description of base model, including parameter estimates and model qualification/diagnostic plots.
 - iii. Description of final model, including parameter estimates and model qualification/diagnostic plots.
- 6. Conclusion

Conclusions will be based on pre-specified hypotheses only. Hypotheses generated during analysis (e.g., from diagnostic plots) will be considered exploratory only.

- 7. Discussion
- 8. Figures
 - a. Figures supporting model selection decisions will be included in the report.
 - b. Typical diagnostic plots will include Conditional Weighted Residuals vs. Time, vs. Conditional Weighted Residuals vs. Prediction, and Observed Dependent Variable vs. Prediction/Individual Prediction.
 - c. VPC (Visual Predictive Check).
 - d. Histogram of post hoc ETAs.
 - e. Observed values vs. individual predicted values.
 - f. Observed values vs. population predicted values.

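### Prespecified PK covariate effects, mainly weight, race and smoking, can be removed at p<0.001 with no planned estimate or interval, and the SAP does not say which p-level supports a formal conclusion

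*SAP*

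**What the plan says.** SAP 9.8.2 states the purpose: "The objectives are to assess the effect of various individual characteristics/covariates" on the PK of the two drugs. SAP 9.8.4 lists ten hypotheses, five per drug: weight on volume, weight on clearance, race on clearance, smoking on clearance, and food on the rate or extent of absorption. On their status it says: "Formal conclusions will be drawn only from these prespecified hypotheses".

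The route into the model is set elsewhere. SAP 9.8.10.3 says: "The impact of individual characteristics on the PK parameters will be explored and included in the population model if significant". SAP 9.8.11 compares nested models by likelihood ratio: "The difference in OFV between two hierarchical or nested models is approximately" chi-square. It then gives the thresholds: "The criteria for forward addition will be p<0.05 and the criteria for backward elimination will be p<0.001". The order is given as "Pre-specified hypotheses will be examined first, followed by hypotheses generated from diagnostic plots", with an automated search afterwards where applicable. The p-value is not the only stated ground for adding a feature; the SAP describes "testing each addition for statistical significance, improvement of diagnostic graphics and/or biological plausibility".

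For reporting, the results part of SAP 9.8.12.1 covers the data, the base model and then "Description of final model, including parameter estimates and model qualification/diagnostic plots". SAP 9.8.13 supplies control and output files for those same two models.

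**The concern.** SAP 9.8.4 gives the ten hypotheses a confirmatory role, but 9.8.11 gives them no route of their own. They are looked at first, and nothing says that they are then protected from backward elimination. An effect with a p-value between 0.001 and 0.05 can be added, removed, and left out of both models that the report must describe.

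The SAP also does not say whether 0.05 or 0.001 supports a formal conclusion. Two analysts following it could reach opposite conclusions on the same effect with p=0.01.

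Assessing a covariate effect needs its size and interval. A verdict that a covariate did not stay in the model does not separate a negligible effect from an imprecisely estimated one.

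**Working it through.** The documents give no power, precision or sample-size basis for these covariate tests, so there is no stated figure to reproduce.

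**Inputs from the SAP.** Entry at p<0.05, elimination at p<0.001, and a likelihood-ratio test on the change in objective function value (OFV) (9.8.11). Ten hypotheses (9.8.4). About 500 subjects (4.2.2).

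**Step 1: OFV change required (chi-square critical values).**

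| Test | To enter (0.05) | To stay (0.001) |
|---|---|---|
| 1 df | 3.84 | 10.83 |
| Race, 3 df (four categories, Protocol 12.4.3) | 7.81 | 16.27 |
| Race, 5 df (six categories, SAP 4.3) | 11.07 | 20.52 |

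**Step 2: chance of staying in, 1 df.** Take Z as normal with mean m and SD 1, and the same statistic at both steps. Power P at two-sided 0.05 gives m = 1.96 + z(P). Retention at 0.001 is approximately 1 − Φ(3.29 − m).

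- 80% power: m = 1.96 + 0.84 = 2.80; 1 − Φ(0.49) = 0.31.
- 90% power: m = 1.96 + 1.28 = 3.24; 1 − Φ(0.05) = 0.48.
- 95% power: retention 0.62.
- 99% power: m = 1.96 + 2.33 = 4.29; 1 − Φ(−1.00) = 0.84.

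For race at 3 or 5 df, a noncentral chi-square gives about 33% and 50% retention at 80% and 90% power. The probability of falling between the two thresholds is 0.80 − 0.31 = 0.49 at 80% power (1 df), and 0.90 − 0.48 = 0.42 at 90%.

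**Step 3: illustration on the clearance scale.** The inputs are assumed, because the documents give none: a two-level covariate with prevalence p, log-scale between-subject SD s, and N = 500. The standard error of the log ratio is s / √(N·p·(1 − p)). With p = 0.15 and s = 0.4, this is 0.4 / √63.75 = 0.050.

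| Clearance ratio | Power at 0.05 | Retention at 0.001 |
|---|---|---|
| 1.15 | 80% | 31% |
| 1.20 | 95% | 64% |
| 1.25 | 99% | 88% |

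Over prevalence 5–25% and SD 0.3–0.5, the ratio needed for 80% retention runs from 1.14 (25%, SD 0.3) to 1.53 (5%, SD 0.5). This treats each subject's clearance as observed with the assumed SD; sparse sampling would lower retention.

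**Step 4: the other reading.** If p<0.05 supports a conclusion, ten independent tests of true nulls give 1 − 0.95^10 = 0.40 for at least one false positive. At p<0.001 the figure is 1 − 0.999^10 = 0.01. The 40% and the 31% belong to opposite readings and cannot both apply.

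**The case against.** The strict elimination level has a purpose: it holds the false-positive risk over ten tests to about 1%. The SAP openly calls its approach traditional, and it matches the protocol's rule of including significant covariates. Significance is also not the sole ground, since diagnostics and plausibility count, and confidence intervals appear among the model-adequacy criteria. All of this stands as a defence of how the final model is built. None of it commits the report to an estimate for a removed prespecified effect.

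Other outputs bear on the objective. The visual predictive check is stratified by all four covariates (SAP 9.8.11.1). Protocol 12.6.9 plans concentration summaries by race, BMI category, smoking and fed/fasted state, although SAP 9.8 does not carry these forward. They help, but they give no adjusted effect on clearance or volume with an interval.

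The food hypotheses are largely outside the point. Fed versus fasted relative bioavailability is a listed primary parameter, if the data allow (SAP 9.8.2), and it is supported by rich crossover data in 28 women (9.8.1, 9.8.6).

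Finally, 9.8.12.1 lists report contents without forbidding more, and its conclusions section must address the prespecified hypotheses. A removed covariate would still receive a verdict, though with no size required.

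**Conclusion.** The gap is real and limited. For weight, race and smoking, no section commits to an estimate and interval when a prespecified effect is removed, and none says which p-level governs a formal conclusion. Modest effects are the ones exposed: about 31% retention at 80% power and 48% at 90%. At 99% power, retention is 84%. These figures rest on a normal approximation, on one statistic serving both steps, and on the elimination rule applying to prespecified effects. The SAP neither says that it does nor exempts them.

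A reader might infer that real covariate effects will simply vanish, or that the substudy objective goes unanswered. The documents do not support that. Strong effects mostly survive, grounds other than the p-value are allowed, food has its own parameter, and the descriptive and graphical outputs partly address the objective. Nor does any section say that a removed covariate will be reported as having no effect.

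The point concerns one of the other secondary objectives and does not touch the Pearl Index or safety. It is worth acting on because the remedy is cheap and needs no new data.

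**What to change.** Keep the stepwise procedure for building the final model. Add to SAP 9.8.11 and 9.8.12.1 that:

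- for each drug, a model with all prespecified covariate effects on the structural base model will be fitted, where identifiable, and the absorption parameter that carries the food effect will be named in advance (9.8.4 now allows either rate or extent);
- every prespecified effect will be reported with its estimate and 95% interval, whatever its p-value and whether or not it stays in the final model, and any non-identifiable term will be reported as such;
- conclusions on the prespecified hypotheses rest on that table, not on survival in the search.

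The cost is SAP wording plus one extra model run and one table per drug. The downside is that some intervals may be wide and some terms not identifiable: SAP 9.8.1 itself warns that this study's data are very sparse, and race needs several coefficients.

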9.8.11.1 Visual Predictive Check

In order to verify that the final model adequately predicts both the central tendency and the variability of the observed data, a visual predictive check (VPC) stratified by weight, race, smoking status, and fed/fasted status will be performed. VPC plots will be made for two or three strata for weight and each stratum for the categorical covariates. For the VPC, simulations will be performed using the final model and final model parameters. The original data set will be used as a template for simulation input. Simulations will be performed to generate approximately 1,000 simulated observations at each time point; if 1,000 simulated observations are not feasible based on the model run times, a reduced number of simulated observations will be used. A graphical comparison will be made between the observed data and the model predicted median and 95% prediction interval over time. Additional VPC plots may be generated to include confidence intervals for the median and prediction intervals of the simulated data. VPC will be conducted in PsN and the result will be summarized using Xpose (Jonsson and Karlsson, 1999).

9.8.12 Reporting

A submission ready report will be developed, as described below.

9.8.12.1 Report Structure

The popPK report will comprise the following sections:

1. Summary

- 2. Objectives and Hypotheses
 - a. Statement of the objectives of the analysis and formal statement of any hypotheses to be tested.
- 3. Assumptions
 - a. List of assumptions, with supporting data, as applicable. Assumptions will not be formally tested.
- 4. Materials and Methods
 - a. Data: description of data, to include (as applicable and appropriate) the number of individuals, number of observations, and range of sample collection times.
 - b. Data analysis methods:
 - i. The methods (e.g., forward addition/backward elimination) and criteria for model selection (likelihood ratio test, diagnostic plots).
- 5. Results
 - a. PopPK results
 - i. Data description: summary statistics including mean, median, and SD of continuous covariates, and distributions of discrete covariates.
 - ii. Description of base model, including parameter estimates and model qualification/diagnostic plots.
 - iii. Description of final model, including parameter estimates and model qualification/diagnostic plots.
- 6. Conclusion

Conclusions will be based on pre-specified hypotheses only. Hypotheses generated during analysis (e.g., from diagnostic plots) will be considered exploratory only.

- 7. Discussion
- 8. Figures
 - a. Figures supporting model selection decisions will be included in the report.
 - b. Typical diagnostic plots will include Conditional Weighted Residuals vs. Time, vs. Conditional Weighted Residuals vs. Prediction, and Observed Dependent Variable vs. Prediction/Individual Prediction.
 - c. VPC (Visual Predictive Check).
 - d. Histogram of post hoc ETAs.
 - e. Observed values vs. individual predicted values.
 - f. Observed values vs. population predicted values.

9.8.13 Source Files

The following documents will be provided as ASCII text files based on the final analysis:

- a. Source data used in the analysis (NONMEM data set).
- b. Base model control file.
- c. Base model output file.
- d. Final Model control file.
- e. Final model output file.

10.0 Validation

Protocol no: MIT-Es0001-C302

PRA's goal is to ensure that each TFL delivery is submitted to the highest level of quality. PRA's quality control procedures will be documented separately in the study specific Quality Control Plan.

12.0 Amendment to the Statistical Analysis Plan

12.1 Amendment 1 from SAP dated 12 December 2016

The key changes to the SAP in amendment 1 are as follows:

- Missing data rules moved to one section for missing data
- The addition of analyses for the Pearl Index to look at the rate of on-treatment pregnancies and on-treatment method failure pregnancies where the at-risk cycles are defined as cycles in which no other methods of birth control are used by the subject
- The addition of an analysis for the Pearl Index to look at the rate of method failure on-treatment
 pregnancies excluding at-risk cycles that were not compliant according to Section 9.4.4 of the
 protocol
- Clarification of the definition of the evaluable cycles for the bleeding analysis in the PP Population in cases where the post Screening biopsy was not performed during Cycle 13
- Addition of criteria for exclusion from the PP Population to exclude cycles within 28 days after prohibited mediations
- Clarification that the Baseline value for the Menstrual Distress Questionnaire is the value collected at Visit 3 as the date of collection is not collected
- Clarification added that compliance by cycle will be based on the cycles defined from the start dates of the cycles per Section 5.1 including detail on how gaps between cycles and overlapping cycles are handled
- Clarification added that for overall compliance only pills reported between the start and stop date for study medication will be included in the numerator
- The addition of actual exposure accounting for days where no pills were taken
- Addition of the number of subjects with bleeding only episodes and spotting only episodes by cycle as endpoints
- Change in the definitions of unscheduled and scheduled bleeding and spotting days to use the episodes
- Clarification added for imputation for missing bleeding data to cover scenarios where 3 or more days having missing data at the end of the diary data collected
- The definition of an evaluable reference period was updated to exclude reference periods where there are gaps between the cycles
- Cumulative absence of withdrawal bleeding rate added as an endpoint

- Bleeding analysis section restructured and split out into the classical cycle analysis (including early and continued withdrawal bleeding as scheduled) which is now classed as the primary definition and the modified analysis (including early and continued withdrawal bleeding as unscheduled) which is no longer classed as the primary definition
- Analyses of bleeding data added for cycles with exactly 1 missed active pill and for cycles with at least 2 missed active pills
- The bleeding analysis by reference period was simplified to no longer differentiate between scheduled and unscheduled bleeding
- Clarification on the scales derived for the Menstrual Distress Questionnaire added
- Enrolled Population definition corrected to use the enrollment date
- PP Population corrected to make it clear that only the PP Population for bleeding is being derived
- Reference to ATC classification removed as data are not coded to ATC in this study
- Clarification added to indicate that BMI will be programmatically derived from height and weight for the vital signs and demography tables
- Listing added for the at-risk cycles for each Pearl Index analysis
- Clarification added to categorize relationship to study medication as not related and related for AEs
- Change to the handling of unscheduled laboratory assessments and clarification added for values above the upper limit of quantification and values below the lower limit of quantification
- Choriogonadotropin beta and eGFR added as laboratory parameters to be summarized
- Addition of summaries and listings of evaluable cycles and reference periods for the bleeding analysis
- Bleeding and spotting analysis section moved to Section 9.5
- Correction to the definition of the alternative definition of at-risk cycles that will be used for the derivation of the Pearl Index for method failure pregnancies based on compliance to indicate that all 8 criteria need to be met for a cycle to be at-risk
- Correction to definition of the presence of a bleeding only unscheduled episode and the presence of a spotting only unscheduled episode for the cycle analysis for bleeding
- Addition of a section for missing or partial dates for AEs
- Addition of a new analysis of the method failure Pearl Index icluding only modified at-risk cycles in the denominator where at-risk cycles will be defined as cycles in which no other methods of birth control (including condoms and emergency contraception) are used by the subject as confirmed in the subject diary where the subject was compliant with the dosing rules 3 to 8 in Section 5.1.1 while cycles with and without confirmed intercourse are being included in the denominator
- Clarification added on how to handle pregnancies for the at-risk cycles when the cycle is not in the diary data
- Clarification added on the handling of partial dates in the diary data
- Addition of summary tables of unscheduled bleeding and spotting days in subjects who had unscheduled bleeding and/or spotting episodes
- Clarification added that the exclusion of cycles for unauthorized medications may be different between the bleeding analysis and contraceptive efficacy
- Clarification added on the inclusion of subjects with an on-treatment or post treatment pregnancy but no diary data in the Safety Population and rules were added on how to derive the start and stop dates for those subjects
- Clarification added that if the subject has an on-treatment pregnancy, then the On-Treatment Period for efficacy ends on the estimated date of conception for that subject
- Addition of summary tables for the number of subjects with a scheduled bleeding episodes starting on each day in the cycle for the classical and modified cycle analysis for bleeding data
- Clarification added that the day for figures of bleeding by day will be the day in the diary data as collected
- WHO drug dictionary version updated
- Update to the prior medications definition for contraceptives

